#### ***Analysis of all treatment emergent serious adverse event(s)***

- All treatment-emergent serious adverse events by primary SOC and PT, showing the number (%) of patients with at least 1 serious treatment-emergent adverse event, sorted by the internationally agreed SOC order and decreasing incidence of PTs within each SOC.

#### ***Analysis of all treatment-emergent adverse event(s) leading to treatment discontinuation***

- All treatment-emergent adverse events leading to treatment discontinuation, by primary SOC and PT, showing the number (%) of patients sorted by the internationally agreed SOC order and decreasing incidence of PTs within each SOC.

#### **2.4.5.2 Deaths**

All deaths reported in the study will be presented as a listing, indicating the date of death, cause of death, whether an autopsy was performed and if yes, autopsy results. Also, any AEs leading to death will be listed.

#### **2.4.5.3 Analyses of laboratory variables**

The summary statistics (including number, mean, median, standard deviation, minimum and maximum) of all laboratory variables (central laboratory values and changes from baseline) will be calculated for each visit or study assessment by age group.

The incidence of PCSAs (list provided in [Appendix A](#)) at any time during the treatment-emergent adverse event period will be summarized by biological function and age group.

#### **2.4.5.4 Analyses of vital sign variables**

The summary statistics (including number, mean, median, standard deviation, minimum and maximum) of all vital signs variables (central laboratory values and changes from baseline) will be calculated for each visit or study assessment by treatment group.

The incidence of PCSAs at any time during the treatment-emergent adverse event period will be summarized by age group.

#### **2.4.5.5 Analyses of electrocardiogram variables**

The summary statistics (including number, mean, median, standard deviation, minimum and maximum) of all ECG variables (central laboratory values and changes from baseline) will be calculated for each visit or study assessment by age group.

The incidence of PCSAs at any time during the treatment-emergent adverse event period will be summarized by age group.

#### **2.4.5.6 Analyses of other safety endpoints**

##### **Anti-rhGAA IgG Antibody, Neutralizing Antibodies, and Other Immunogenicity Testing**

Anti-rhGAA IgG antibody titer values will be summarized using summary statistics. All data will be presented in listings for each patient.

By patient listings will also display results of inhibitory/neutralizing antibody, circulating immune complex, anti-rhGAA IgE antibody, serum tryptase activity, complement activation, and skin testing performed. Descriptive summaries may also be provided as appropriate.

##### **Infusion associated reactions**

Summary table of IARs by SOC and PT will be presented. A detailed listing of patients who experience IARs including information on severity, relationship to treatment, timing from first infusion to the onset of the IAR, action taken regarding study treatment, other action taken, and patient outcome, will be provided.

#### **2.4.6 Analyses of pharmacokinetic variables**

Alglucosidase alfa concentration values below the plasma assay limit will be treated as zero in calculating mean values. Mean values below LLOQ will be reported as LLOQ in the tables and not plotted in the figures if after  $C_{max}$ .

Plasma concentrations and pharmacokinetic parameters will be summarized by arithmetic mean, geometric mean, standard deviation, coefficient of variation (CV (%)), minimum, median, maximum, and number of observations by age groups and study visits (if applicable).

#### **2.4.7 Analysis of pharmacokinetics and immunogenicity**

To evaluate the effect of immunogenicity on the PK of alglucosidase alfa, pre-dose IgG and inhibitory/neutralizing antibody titers for each patient will be analyzed graphically with respect to PK parameters for Day 1.

The relationship between anti-rhGAA antibody titers and the PK of alglucosidase alfa will be presented by summary of the assessed PK parameters grouped by anti-rhGAA antibody negative subjects, anti-rhGAA antibody positive subjects and anti-rhGAA antibody positive subjects with IgG inhibitory/neutralizing antibodies to alglucosidase alfa.

If data allows, anti-rhGAA antibody titers will be plotted against the assessed PK parameters.'

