## **8 TREATMENTS**

### **8.1 Treatments Administered**

Alglucosidase alfa will be administered by IV infusion at a dose of 20 mg/kg body weight. Infusion will be administered in a step-wise manner. It is recommended that the infusion be administered at an initial rate of approximately 1 mg/kg/hr and may be augmented by 2 mg/kg/hr every 30 minutes, if there are no signs of IARs, until a maximum rate of approximately 7 mg/kg/hr is reached. The infusion length will be dependent on the dose. The length of infusion is approximately 4 hours. Specific details pertaining to the infusion volumes and rates can be found in the Pharmacy Manual.

Guidelines for management of IARs can be found in the Study Operations Manual (SOM).

Patients will be monitored for AEs for 2 hours after infusion. Patients may be required to stay for a longer observation period at the Investigator's discretion.

A central venous catheter is recommended for delivery of the investigational drug but placement will be at the discretion of the Investigator. Medical personnel authorized by the Investigator will be responsible for the administration of medication throughout the study.

Safety will be evaluated in consultation with the DSMB on an ad hoc basis. An immunologist will be consulted, when necessary, to review information and provide treatment recommendations for IARs.

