## **12.9 Other Analyses**

### **12.9.1 Pharmacokinetic Endpoints**

Pharmacokinetic assessments will be conducted using a validated assay. Plasma concentration-time data will be analyzed using non-compartmental methods in accordance with Genzyme Guideline for Non-compartmental Analysis of Pharmacokinetic Data. Actual dosing and sampling timepoints will be used for data analysis. The following PK parameters will be assessed if data permit:  $C_{max}$ ,  $T_{max}$ ,  $AUC_{last}$ ,  $AUC_{inf}$ ,  $T_{1/2}$ , CL and  $V_d$ . Based on previous data, no accumulation of drug is expected upon repeat dosing; hence, the PK analyses will treat all data as coming from single dose administrations.

If data do not lend to non-compartmental analysis, model-based approaches such as nonlinear mixed effects modeling may be utilized for data analysis.

Individual assessments and descriptive statistics (mean, SD, median, minimum, maximum, geometric mean and percent coefficient of variation) will be presented for plasma concentration time data and PK parameters. Individual and mean (SD) plasma concentration time profile will be presented graphically.

To evaluate the effect of immunogenicity on the PK of alglucosidase alfa, pre-dose IgG and inhibitory/neutralizing antibody titers for each patient will be analyzed graphically with respect to clearance for Day 1. If relationships are apparent, further quantitative/statistical analysis may be performed (e.g., statistical significance, correlation coefficients).

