## **1.5 MODIFICATIONS TO THE STATISTICAL SECTION OF THE PROTOCOL**

Not applicable.

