#### 2.1.5 Pharmacokinetic variables

Blood samples will be collected at pre-dose (prior to infusion); immediately (within a few minutes) before the infusion rate changes from 1 to 3 mg/kg/hr, from 3 to 5 mg/kg/hr, and from 5 to 7 mg/kg/hr; immediately before the end of infusion; and at 1, 2, 4, 8, 12, and 24 hours after infusion (times from end of infusion) on Day 1. In case of IAR, IAR(s) should be appropriately managed and PK sample has to be collected before any first time increase in infusion rate from 1 to 3 mg/kg/hr, from 3 to 5 mg/kg/hr, and from 5 to 7 mg/kg/hr achieved during administration of the remaining dose, immediately before the end of infusion; and at 1, 2, 4, 8, 12, and 24 hours after end of infusion. A maximum of 11 blood samples (1 mL each) will be drawn for PK sampling. Per patient, the trial-related blood loss (including any losses in the maneuver) should not exceed 3% of the total blood volume during a period of 4 weeks or 1% at a single time.

Actual dosing and sampling timepoints must be recorded for all days when blood sampling for pharmacokinetics occurs.

From the plasma concentration time data, the following pharmacokinetic parameters will be assessed:

$C_{max}$	The maximum observed concentration
$T_{max}$	The actual sampling time to reach maximum observed concentration
$AUC_{0-last}$	Area under the concentration-time curve from time 0 to the time of the last quantifiable concentration

If data permit,

AUC	Area under the concentration-time curve from time 0 and extrapolated to infinite time
$T_{1/2}$	Terminal elimination half-life
CL	Total systemic clearance
Vd	Volume of distribution

Additional parameters may be analyzed and reported, as appropriate. Industry standard, validated software such as WinNonlin® or Phoenix NLME® will be used for PK data analysis.

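### The antibody-group summaries of Cmax and Tmax cannot tell an antibody effect from a slower infusion, and the protocol and SAP disagree on which PK parameters the antibody analysis covers

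*SAP*

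**What the plan says.** **Scope of the antibody analysis.** In Protocol 12.9.1, pre-dose IgG and "inhibitory/neutralizing antibody titers for each patient will be analyzed graphically with respect to clearance for Day 1". In SAP 2.4.7 the same titers "will be analyzed graphically with respect to PK parameters for Day 1", and there is also a "summary of the assessed PK parameters grouped by anti-rhGAA antibody negative subjects", antibody-positive subjects, and positive subjects with inhibitory/neutralizing antibodies. SAP 2.1.5 lists the assessed parameters. They include Cmax ("The maximum observed concentration") and Tmax ("The actual sampling time to reach maximum observed concentration") as well as AUC, half-life, clearance (CL) and volume. SAP 1.5, on modifications to the protocol's statistical section, reads "Not applicable", and SAP 1.6 says the same.

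The protocol is not uniform. Its synopsis sets PK parameters in general against antibody titers, and 6.1.3 speaks of the effect of antibodies on the PK without singling out clearance.

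**Infusion rate.** Protocol 8.1: "It is recommended that the infusion be administered at an initial rate of approximately 1 mg/kg/hr". Steps of 2 mg/kg/hr every 30 minutes, up to about 7 mg/kg/hr, follow only in the absence of reactions. Protocol 8.4 recognises that a reaction may call for a lower rate, and 9.5 has a sampling rule for infusions affected by a reaction.

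**Use of infusion data.** Protocol 8.7 says incomplete infusions will be considered in the analysis. SAP 2.4.3 lists the dose sequence and cumulative dose. Neither SAP 2.4.6 nor 2.4.7 uses infusion duration or marks an infusion that was slowed or interrupted but completed.

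**The concern.** The secondary objective is the relation between antibody titers and PK. Under linear kinetics true clearance does not depend on how fast the dose is given, but Cmax and Tmax do. Two patients with identical disposition and the full 20 mg/kg can differ widely on both if one infusion is slowed after a reaction. If such slowing were commoner among antibody-positive patients, the SAP 2.4.7 table would show lower Cmax and later Tmax in that group with no antibody effect on disposition. No planned PK table or plot would tell the reader which explanation applies. The age-group summaries in SAP 2.4.6 mix infusion profiles in the same way.

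**Working it through.** **Inputs from the documents.** Dose 20 mg/kg and rate steps 1, 3, 5, 7 mg/kg/hr of 30 minutes each (Protocol 8.1); samples before each rate change, at end of infusion, and 1, 2, 4, 8, 12 and 24 h later (Protocol 9.5).

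**Assumptions.** One-compartment linear PK, the same clearance and volume V in every scenario, and a half-life of 1 to 4 h (the documents give none).

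**Step 1: the plan's own figure.** The first three steps deliver 0.5 × (1 + 3 + 5) = 4.5 mg/kg in 1.5 h. The remaining 15.5 mg/kg takes 15.5/7 = 2.21 h. The total is 3.71 h, consistent with the stated length of about 4 hours.

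**Step 2: same dose, altered infusion.**
- Held at 5 mg/kg/hr: 1 + 18/5 = 4.60 h.
- Held at 3 mg/kg/hr: 0.5 + 19.5/3 = 7.00 h.
- 2 h stop after one hour at 7 mg/kg/hr: 3.71 + 2 = 5.71 h.

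**Step 3: Cmax and Tmax.** Over a segment of length d at rate R, with k = ln 2 / half-life:

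C(end) = C(start)·e^(−kd) + (R/(Vk))·(1 − e^(−kd)).

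Example with half-life 2 h (k = 0.3466) and V = 1. On the recommended scheme the concentration is 3.778 at 1.5 h. At the end it is 3.778 × 0.464 + (7/0.3466) × 0.536 = 12.58. Held at 3, it is 0.459 at 0.5 h. At the end it is 0.459 × 0.105 + (3/0.3466) × 0.895 = 7.79. The ratio is 7.79/12.58 = 0.62. The highest scheduled sample is the end-of-infusion sample in every scenario below, so Tmax equals infusion length.

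**Step 4: computed clearance.** CL = dose/AUCinf, from the scheduled samples by linear-up/log-down trapezoids with the terminal slope taken as known. Held at 3, there is no sample between 0.5 h and 7.0 h, so a straight line undercuts the rising curve, AUC reads low and CL high. With the stop, the line from 1.5 h to 5.71 h bridges the dip and CL reads low.

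Ratios to the recommended scheme (true CL ratio is 1.00 throughout):

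| Scenario | Tmax (h) | Cmax ratio, half-life 1 / 2 / 3 / 4 h | Computed CL ratio, half-life 1 / 2 / 3 / 4 h |
|---|---|---|---|
| Recommended | 3.71 | 1.00 | 1.00 |
| Held at 5 | 4.60 | 0.78 / 0.86 / 0.90 / 0.92 | 1.08 / 1.04 / 1.02 / 1.01 |
| Held at 3 | 7.00 | 0.50 / 0.62 / 0.70 / 0.76 | 1.27 / 1.14 / 1.08 / 1.05 |
| 2 h stop | 5.71 | 0.75 / 0.78 / 0.82 / 0.85 | 0.87 / 0.96 / 0.98 / 0.99 |

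**Step 5: from patient to group.** If a share p of each group is held at 3 and the individual Cmax ratio is r, the ratio of geometric means (positive to negative) is r^(p₊ − p₋). The shares are assumed.
- 30% against 10%: 0.50^0.2 = 0.87 to 0.76^0.2 = 0.95. Mean Tmax shifts by 0.2 × (7.00 − 3.71) = 0.66 h.
- 50% against 10%: 0.50^0.4 = 0.76 to 0.76^0.4 = 0.89.
- Equal shares: 1.00.

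**The case against.** A reader might infer that the SAP alone widened the analysis. It did not: the synopsis and 6.1.3 already cover PK generally, and clearance remains an assessed parameter under SAP 2.4.7. What stands is that 12.9.1 disagrees with all three and that SAP 1.5 and 1.6 do not mention it.

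A reader might also infer that the antibody-positive group will show a spurious fall in Cmax. Nothing in the documents says those patients react more or are infused more slowly, and equal slowing gives no difference. The analysis is descriptive, in about 20 patients, with no tests and no decision resting on Cmax. Clearance beside Cmax would help a careful reader. This objection stands: the confounding is possible, not demonstrated, and the risk is one of interpretation.

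A third reading is that clearance is free of the problem, so Cmax and Tmax should be shown only for undisturbed infusions. Neither part holds. Computed clearance also shifts, though less than Cmax, and it is reported only if the data permit. Restricting to undisturbed infusions selects on an event after the pre-dose titer. If antibodies cause reactions, that removes the most affected patients and can itself bias the comparison.

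Finally, much of the raw information is already planned: actual dosing times, the dose-sequence listing, reaction listings with timing and action taken, and individual profiles. That keeps the fix cheap. It does not supply it, because no PK output brings the pieces together.

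**Conclusion.** The concern holds in a limited form. The scope of the antibody analysis differs between Protocol 12.9.1 and the synopsis, 6.1.3 and SAP 2.4.7, and should be reconciled. Separately, the planned antibody-group summaries of Cmax and Tmax could not distinguish an antibody effect from slower infusion if slowing differs by group.

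For an individual held at 3 mg/kg/hr the effect is large: Cmax 24% to 50% lower and Tmax about 3.3 h later, with true clearance unchanged. For a group it depends on unknown shares: a Cmax ratio of 0.87 to 0.95 at an assumed 30% against 10%, and 1.00 at equal shares. Computed clearance is less affected but not immune, about 5% to 27% high when held at 3 and 1% to 13% low with a 2 h stop. All these ratios rest on one-compartment linear kinetics and the assumed half-life of 1 to 4 h.

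**What to change.** - **Reconcile the scope.** Align Protocol 12.9.1, the synopsis, 6.1.3 and SAP 2.4.7, and record the departure from 12.9.1 in SAP 1.5 or 1.6.
- **SAP 2.4.7.** Name CL, where estimable, as the main antibody-PK parameter, with dose-normalised AUC as support. Dose-normalised AUCinf is simply 1/CL, so AUClast is the useful version where CL cannot be estimated. Note that CL from the sparse samples during infusion also moves with the infusion profile.
- **SAP 2.4.6 and 2.4.7.** Add actual infusion duration and a slowed/interrupted flag to the PK listing and tables, and mark flagged patients on the plots. Show Cmax, Tmax and CL for all patients and again without flagged patients. Keep the all-patient display, and do not limit the comparison to undisturbed infusions.

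The cost is SAP wording, one derived flag and a few extra displays. Protocol 9.5 and SAP 2.1.5 already require actual dosing times, so no new data collection appears necessary. The downside is small subgroups: about 20 patients across three antibody categories, fewer once flagged patients are left out.

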## **7 PATIENT POPULATION AND SELECTION**

### **7.1 Inclusion Criteria**

A patient must meet all of the following criteria to be eligible for this study.

1. The patient and/or the patient's parent/legal guardian is willing and able to provide signed informed consent.
2. The patient has a confirmed GAA enzyme deficiency from skin, blood, or muscle tissue and/or 2 confirmed GAA gene mutations.
  - 2.1 Infant and toddler Pompe disease patients can be included in the study only under condition (minimal body weight) that the trial-related blood loss (including any losses in the maneuver) will not exceed 3% of the total blood volume during a period of 4 weeks and will not exceed 1% at any single time.
3. The patient, if female and of childbearing potential, must have a negative pregnancy test (urine beta-human chorionic gonadotropin) at screening. Note: All female patients of childbearing potential and sexually mature males must agree to use a medically accepted method of contraception throughout the study.
4. For patients previously treated with alglucosidase alfa the patient has received alglucosidase alfa for at least 6 months.

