### **1.3 DETERMINATION OF SAMPLE SIZE**

Approximately 20 patients will be enrolled in this study (10 patients <18 years old and 10 patients  $\geq$ 18 years old). This study is not powered to make any statistical inferences.

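### The scale of CL and Vd (absolute or per kg) is not stated, and the antibody comparison drops the age split, so body size could mimic or mask an antibody effect on these two parameters

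*SAP*

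**What the plan says.** SAP 2.1.5 and Protocol 9.5 list the PK parameters by name only. CL is "Total systemic clearance" and Vd is "Volume of distribution". No unit, per-kg form or weight covariate appears. SAP 2.5.1 announces formulas for computing parameters, but the only one that follows is for age.

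Three places use these parameters:

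- **SAP 2.4.6** summarises concentrations and PK parameters by age group.
- **SAP 2.4.7** says the titer–PK relationship "will be presented by summary of the assessed PK parameters grouped by anti-rhGAA antibody negative subjects", then by antibody-positive patients and by positives with inhibitory/neutralizing antibodies. It also plans plots of titers against the PK parameters. No age or weight stratum is mentioned.
- **Protocol 12.9.1** says pre-dose titers "will be analyzed graphically with respect to clearance for Day 1". If a relationship is apparent, correlation or significance analysis may follow.

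On the population, Protocol 7.1 says "Infant and toddler Pompe disease patients can be included in the study", subject to blood-loss limits. The target is about 20 patients, half under 18 and half 18 or older (SAP 1.3). Weight is recorded at screening (Protocol 9.2, Appendix A) and summarised at baseline (SAP 2.4.1), but no planned PK analysis uses it.

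**The concern.** Absolute clearance and volume generally rise with body size. A group with more adults will then show larger absolute CL and Vd than a group with more children, whatever antibodies do. SAP 2.4.7 contrasts antibody groups across all ages with nothing to separate size from antibody status.

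Uneven antibody status is a realistic prospect. Protocol 6.3 explains that naïve and previously treated patients are both enrolled because of the antibody objective. The only enrolment target is on age, so nothing balances treatment history or antibody status over age or weight. With about 20 patients, imbalance could also arise by chance.

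What is at stake is the reading of clearance, the parameter that Protocol 12.9.1 names for the secondary objective. A size artefact could also prompt the optional correlation or significance analysis described there, and size variation could hide a real relationship.

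**Working it through.** The plan gives no figure to reproduce: there is no sample-size calculation, and no assumed CL or variability. What follows is an illustration.

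**Inputs from the documents:** 10 patients under 18 and 10 aged 18 or over; dose 20 mg/kg; 11 PK samples of 1 mL; blood loss at most 3% of total volume over 4 weeks.

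**Assumptions not in the documents:** adults 70 kg; children 10, 20 or 30 kg; 12 antibody-positive and 8 negative patients; CL proportional to weight^b with b = 1 or 0.75; no true antibody effect; 70 to 90 mL blood per kg.

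**Step 1, how small a patient could be.** 11 mL / 0.03 = 367 mL total blood. That corresponds to 367/90 = 4.1 kg up to 367/70 = 5.2 kg. Other blood draws and losses raise this floor, so it is the edge of eligibility and not a typical patient.

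**Step 2, one worked case.** Children 20 kg, 4 of 10 positive; adults 70 kg, 8 of 10 positive. Arithmetic means are in relative units.

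- Absolute CL, b = 1: positives (8×70 + 4×20)/12 = 53.3; negatives (2×70 + 6×20)/8 = 32.5; ratio **1.64**.
- Absolute CL, b = 0.75 (70^0.75 = 24.20, 20^0.75 = 9.46): positives 19.29; negatives 13.14; ratio **1.47**.
- CL per kg, b = 1: ratio **1.00**.
- CL per kg, b = 0.75 (70^-0.25 = 0.346, 20^-0.25 = 0.473): positives 0.388; negatives 0.441; ratio **0.88**.

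**Step 3, other mixes, using geometric means.** Ratio for absolute CL = (child weight / adult weight)^(b × (child share in positives − child share in negatives)). For CL per kg, replace b by b − 1.

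| Children/adults in positives; in negatives | Child weight | Absolute, b=1 | Absolute, b=0.75 | Per kg, b=1 | Per kg, b=0.75 |
|---|---|---|---|---|---|
| 4/8; 6/2 | 10 kg | 2.25 | 1.84 | 1.00 | 0.82 |
| 4/8; 6/2 | 20 kg | 1.69 | 1.48 | 1.00 | 0.88 |
| 4/8; 6/2 | 30 kg | 1.42 | 1.30 | 1.00 | 0.92 |
| 7/5; 3/5 | 20 kg | 0.77 | 0.82 | 1.00 | 1.07 |
| 8/4; 2/6 | 10 kg | 0.44 | 0.54 | 1.00 | 1.22 |
| 8/4; 2/6 | 20 kg | 0.59 | 0.68 | 1.00 | 1.14 |
| 8/4; 2/6 | 30 kg | 0.70 | 0.77 | 1.00 | 1.09 |
| 6/6; 4/4 (equal mix) | any | 1.00 | 1.00 | 1.00 | 1.00 |

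The false ratio can go either way, and it vanishes when the age mix is equal. The same arithmetic applies to Vd for whatever weight exponent Vd follows.

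**Step 4, what AUCinf adds.** For a full dose, AUCinf = 20 × weight / CL = 20 / (CL per kg). In the 20 kg case with mix 4/8; 6/2, size alone gives a CL ratio of 1.69 with an AUCinf ratio of 1.00 (b = 1), or 1.48 with 1/0.88 = 1.14 (b = 0.75). A true antibody effect raising CL by those factors would instead lower AUCinf to 1/1.69 = 0.59 or 1/1.48 = 0.68. The two explanations can therefore be told apart if CL and AUCinf are read together.

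**The case against.** A reader might infer that the plan defines CL and Vd as absolute values. It does not. It gives names without units, and CL computed from a dose entered as 20 mg/kg would come out per kg. Protocol 12.9.1 defers non-compartmental analysis to a sponsor guideline whose content is not given, and SAP 2.1.5 allows additional parameters. These clauses permit weight normalisation but do not commit to it. What stands is that the scale is unspecified.

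A reader might also infer that the whole antibody analysis is confounded by size. That goes too far. SAP 2.4.7 covers all assessed PK parameters, and AUCinf at the full dose already carries per-kg clearance information (step 4). AUCinf is reported only if data permit, but so is CL. Cmax, AUC and half-life are much less exposed. The AUCinf argument weakens only for incomplete or changed doses.

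Nor do the documents show that bias will occur. They do not link antibody status to age, and the weights and splits above are assumed. The main PK summary in SAP 2.4.6 is by age group, so all-age pooling is specific to 2.4.7 and to Protocol 12.9.1, which is silent on age.

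Finally, the analysis is descriptive, with no formal inferential tests planned (SAP 2.4) and individual PK results presented (Protocol 12.9.1). No error rate or decision rule is affected. All of this narrows the point. It does not supply the missing units or the missing age split.

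**Conclusion.** The point holds as a conditional one. The documents leave the scale of CL and Vd open, and the antibody comparison has no control for age or weight on either scale. If the values are absolute and antibody status is unevenly spread over age or weight, size alone can shift CL between antibody groups. Under the assumptions above, the geometric mean ratio ranges from 0.44 to 2.25, against 0.82 to 1.22 per kg. Without imbalance it is 1.00. The consequence is possible misreading of the CL and Vd displays in a descriptive secondary analysis. Clarifying this before database lock is worthwhile and inexpensive.

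**What to change.** - In SAP 2.1.5, define CL and Vd per kg, with units, using the recorded weight. Use these in the 2.4.6 and 2.4.7 summaries and plots, and keep absolute values in listings.
- In SAP 2.4.7, mark age group (<18, ≥18) on the titer plots, and show the antibody-group summaries by age group as well as overall. Per-kg scaling alone can leave a residual size difference (0.88 in the worked case).
- State that any CL difference between antibody groups will be read alongside AUCinf, noting patients with incomplete or changed doses.

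The cost is SAP wording and programming; weight and age are already collected. The downside is small cells when about 20 patients are split by age and antibody status. The under-18 group can also still mix infants with adolescents, so individual values should stay visible.
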